**Figure 1. Four Step Screening Process: Summary of Exclusion Criteria by Steps**

For this within-subject placebo-controlled partially-blinded treatment protocol (Fig 2), we will enroll 48 medically stable Veterans with stabilized recovery trajectories after a stroke or a TBI and who have a homogeneous level of moderately impaired cognitive function persisting after standard rehabilitation.

An equal number of Veterans with stroke/TBI (24-stroke; 24-TBI) will be enrolled, but we will over-sample females (Figure 2). For each iTBS group to include an equal number of Veterans with stroke/TBI, Veterans will be randomly assigned by diagnostic groups, to receive Active iTBS or Placebo iTBS. To measure immediate effects (ImE), an equal number of Veterans with stroke/TBI within each iTBS group will be randomly assigned to be tested with the Modified Digit Span (MDS) or AMPS, three times at 30 min intervals. Persisting effects (PE) tests will be administered to all participants at five timepoints including prior to and after Active iTBS or Placebo iTBS and 2-weeks later prior to the 2nd intervention, where all Veterans receive APT paired with their assigned iTBS (Active iTBS + APT or Placebo iTBS + APT). The alternate ImE test is then administered three times at 30 min intervals, followed by re-administration of all PE tests. Two weeks later, all PE tests are administered a 5th time (B4). ImE and PE measures are used to define magnitude and duration of cognitive change. Randomization (SAS Proc Plan) will be managed by one un-blinded researcher who will not provide interventions or conduct testing.

**Figure 2. Study Design (ImE = Immediate Effects Tests; AMPS = AMPS or MDS = Modified Digit Span; PE = Persisting Effects Tests for all participants; Study Day-1: Obtain Covariates and Treatment preparation information; B0 = Pre-Study-Day-2; B1 = Post-Study-Day-2; After 2-Weeks B2 = Pre-Study-Day-3; B3 = Post-Study-Day-3; After 2-Weeks B4 = Study-Day 4)**

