The Repeatable Battery for the Assessment of Neuropsychological Status (RBANS) will be used to broadly assess a range of cognitive domains (e.g., Learning/Immediate Memory, Language, Attention) whereas the Wechsler Adult Intelligence Scale (WAIS-IV) Digit Span subtest will be used to measure working memory. The Delis-Kaplan Executive Functioning System (DKEFS) Color-Word Interference subtest will be used to measure processing speed and executive function whereas the Behavior Rating Inventory of Executive Function (BRIEF) will be used to measure the Veteran's perception of executive function across nine domains as well as overall executive functioning, behavioral regulation, and metacognition. We will also examine testing validity in terms of inadequate effort using the Dot Counting Test and response validity using the BRIEF.

We define moderately impaired cognitive capacity as having two or more scores falling  $\geq 1$  standard deviation below age normed expectations on: the RBANS index scores, DKEFS Color-Word Trials 3 and 4 scale scores, and/or WAIS-IV Digit Span scaled score. Any Veteran with a RBANS Total Scale  $< 70$  will be excluded as this cut-off point suggests likely presence of severe cognitive impairment or major neurocognitive disorder. Any Veteran with DOT (E-score:  $\geq 17$ ) or BRIEF-A scores (Negativity  $\geq 6$ ; Infrequency  $\geq 3$ ; Inconsistency  $\geq 8$ ) indicative of questionable testing validity will be excluded. The use of these test performance criteria will identify Veterans who are not employable and are struggling with day to day life requiring assistance with complex Independent Activities of Daily Living due to cognitive impairments.

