For measuring immediate changes in cognitive function, we will use the aforementioned **AMPS**. For each of the *three administrations, in 30-min intervals*, a unique task will be randomly selected (without replacement) from the set of tasks developed during Step 4 (Fig 1). Thus, the same IADL is never repeated for the same Veteran.

**Persisting Effects (PE) Measures.** This battery includes the same five tests/sub-tests administered during screening (Fig 1, Step-4: AMPS, RBANS, WAIS-IV Digit Span, DKEFS subtests and BRIEF-A). As the BRIEF-A will be re-administered, the study Neuropsychologist will review BRIEF-A scores and, if there are compelling reasons, Veterans with scores suggesting atypical validity will be withdrawn. This battery also includes tests to measure change in mood: Columbia Suicide Severity Rating Scale (C-SSRS) *Beck Anxiety Inventory (BAI)*, and the *Posttraumatic Stress Disorder Checklist (PCL)*. To assess fatigue, we will use the Fatigue Severity Scale (FSS), which is a self-report measure of prior-week fatigue during nine activities and current fatigue. To measure behavioral features of agitation, we will use the *Agitated Behavioral Scale (ABS)*.

Table 2: Instrumentation: Testing Battery					
Immediate Outcome Effects (ImE)	Hrs/Admin	Aims	Variable Types	# Reps	
AMPS	1.5	1 & 2	Continuous (logit)	3	
Modified Digit Span (MDS)	0.2	1 & 2	Proportional (% correct)	3	
Persisting Effects Testing Battery (PE)	Hrs/Admin	Aims	Variable Types	# Reps	
Repeatable Battery for Assessment of Neuropsych Status (RBANS)	1.0	2	Continuous (normed score)	5	
Weschler Adult Intelligence Scale (WAIS-IV) Digit Span			Proportional (% correct)	5	
Delis-Kaplan Executive Functioning System (DKEFS): Color-Word			Continuous (normed score)	5	
Behavior Rating Inventory of Executive Function (BRIEF)			Continuous (normed score)	5	
AMPS	1.5	2	Continuous (logit)	5	
PTSD Checklist (PCL)	0.1	2 & 3	Mean # symptoms/ severity	5	
Columbia Suicide Severity Rating Scale (C-SSRS)	0.1	2 & 3	Raw score (Veteran rating)	5	
Beck Anxiety Inventory (BAI)	0.1	2 & 3	Raw score (Veteran rating)	5	
Agitated Behavior Scale (ABS)	0.1	2 & 3	Raw score (research clinician rating)	5	
Fatigue Severity Scale (FSS): Prior Week Daily Living Score	0.1	2 & 3	Raw score (Veteran rating)	5	
Fatigue Severity Scale (FSS) L VASF Current Fatigue Rating	0.1	2 & 3	Raw score (Veteran rating)	5	

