Average Placebo iTBS + APT MCG using t-tests for continuous data and z-tests for binary data. Using MLM, we will also determine if Active iTBS is related to more MDS or more AMPS gains. The group (Active iTBS or Placebo iTBS) by time interaction parameter will be used to examine if Active iTBS has a differential trend compared to Placebo iTBS. For 2i, we will also use MLM to identify presence of an additive effect of APT by examining Active iTBS + APT trend lines. For both the AMPS and the MDS outcomes, the group (Active iTBS + APT or Placebo iTBS + APT) by time interaction parameter will be used to examine if the Active iTBS + APT has a differential trend compared to Placebo iTBS + APT. For each intervention we will also determine (2ii) presence of persisting effects of Active iTBS and Active iTBS + APT in the short-term, long-term and cumulatively. Using the PE measures specified in Table 1 and t-tests, we will compare each PE measure for Active iTBS with Placebo iTBS and for Active iTBS + APT with Placebo iTBS + APT. Significant results will be reported. For (2iii), we will use one-tailed t-tests to identify presence of practice effects for MDS and AMPS. We will compare MDS and AMPS average peak gains after Placebo iTBS with average peak gains after Active iTBS. If the average Placebo iTBS peak gain is greater than the average Active iTBS peak gain for either MDS or AMPS, then we will repeat analyses above (for 2i and 2ii) using ImE and PE measures after adjusting them for the detected practice effects.

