For Aim 3, we will compute study attrition as percent of participants dropping out after Study-Day 2 and after Study-Day 3. We will examine whether or not these attrition rates differ (3i) by stroke and TBI groups using chi-square. To examine if Veteran's with stroke and TBI have (3ii) different perceptions regarding the suitability of the number and type of tests and number of study-days, we will compare each group's average ratings, by suitability index, using t-tests. To explore the relationship between perceived suitability and fatigue as well as mood (3iii), we will compute Pearson correlations at each of the 5-timepoints (B0 through B4) between average ratings of suitability indices 1 through 3 and averages for each of the two fatigue measures and each of the five mood measures [5x (3x2) + 5x (3x5) = 105 correlations]. We will also compute correlations for average suitability indices 7 through 8 collected on Study-Day 4 (B4) with the averages from that same day for each of the two fatigue measures and each of the five mood measures [1x (2x2) + 1x (2x5) = 14 correlations]. We will test the significance of each correlation using Fisher Z test and results will be interpreted accordingly.

Aims 2 and 3 involve multiple comparisons. Bonferroni correction of type I error rate is very conservative, and, at this early research stage, it could mask important findings. Thus, we will control for false discovery rate (FDR) using an FDR level of .05.

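### Discretionary withdrawal on repeat BRIEF-A validity scores can remove treated Veterans from all later outcomes, which can bias the arm comparisons and may inflate attrition

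*Combined protocol and SAP*

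**What the plan says.** **The instrument.** Of the persisting-effects (PE) battery, Section 5.5 says: "This battery includes the same five tests/sub-tests administered during screening". The BRIEF-A is one of the five. Table 2 places it in the Aim 2 part of that battery as a normed score with 5 repetitions.

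**The timing.** Section 5.1 (text under Figure 1): "Persisting effects (PE) tests will be administered to all participants at five timepoints including prior to and after Active iTBS or Placebo iTBS". B0 precedes the first iTBS session. B1 closes Study-Day 2, B2 and B3 open and close Study-Day 3, and B4 is Study-Day 4.

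**The rule.** Section 5.5 has the study Neuropsychologist review the repeat scores, and "if there are compelling reasons, Veterans with scores suggesting atypical validity will be withdrawn". At screening the rule is different in kind: fixed limits (Negativity ≥ 6, Infrequency ≥ 3, Inconsistency ≥ 8), and Veterans with scores "indicative of questionable testing validity will be excluded".

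**The consequences.** Section 5.7 keeps data collected before withdrawal and allows replacement only before any procedure past the baseline measures. For the PE outcomes in Section 5.6, "we will compare each PE measure for Active iTBS with Placebo iTBS" by t-test. No analysis set or missing-data method is given. For Aim 3, "we will compute study attrition as percent of participants dropping out after Study-Day 2 and after Study-Day 3", and then "We will examine whether or not these attrition rates differ (3i) by stroke and TBI groups using chi-square".

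**The concern.** Once Veterans have been assigned and treated, removing some of them on something measured after treatment means that the remaining groups are no longer simply the randomized groups. Here the trigger comes from a questionnaire that is also an outcome instrument, and the decision is discretionary. Whether the reviewer knows the arm is not stated.

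The reach of the rule is also out of proportion to its cause. A doubtful self-report form calls that form into question. It does not call into question the AMPS, MDS, RBANS, DKEFS or Digit Span, yet withdrawal ends collection of all of them. Neither the rules for stopping iTBS or study participation (Section 5.1) nor the investigator's withdrawal reasons (Section 5.7) mention test validity, so the rule is not presented as a safety measure.

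Three things are at stake: the later Active/Placebo comparisons, a sample size with almost no spare completers, and an attrition result that Aim 3 relates to how suitable Veterans find the study.

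**Working it through.** **1. What a withdrawal removes.** From the visit schedule in Section 5.1 and the retention rule in Section 5.7:

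| Review that triggers withdrawal | Main-study data lost |
|---|---|
| B0 | All treatment-phase data, but before treatment; may be replaceable |
| B1 | B2, Study-Day 3 immediate effects, B3, B4 |
| B2 | Study-Day 3 immediate effects, B3, B4 |
| B3 | B4 |
| B4 | None |

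The Study-Day 2 immediate-effects tests come before B1, so no post-treatment review can remove them. The B0-to-B1 contrast also survives.

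**2. The plan's own sample size.** Inputs from Section 5.6: effect size 0.90, 80% power, 21 per group, 12% attrition, 48 enrolled. Alpha is not stated there. A two-sided 0.05 t-test gives 20.39, so 21 per group (one-sided gives 16). Power at 21 per group is 81.2%. Then 42 / 0.88 = 47.7, so 48. The plan's figures reproduce.

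**3. Power if validity withdrawals come on top of the 12% allowance** (losses spread over both arms):

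| Extra withdrawals | Completers | Power |
|---|---|---|
| 0 | 42 | 81.2% |
| 1 | 41 | 80.2% |
| 2 | 40 | 79.2% |
| 4 | 38 | 77.0% |
| 6 | 36 | 74.6% |

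**4. Bias in the arm difference.** Suppose a normally distributed flag score has correlation r with poor outcome, and fractions p1 and p0 are withdrawn in the two arms. The complete-case difference then shifts by

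r × [φ(z1)/(1 − p1) − φ(z0)/(1 − p0)],

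where φ is the standard normal density and z the cut-off that withdraws fraction p. If p1 = p0, the bracket is zero. If r = 0, the shift is zero.

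- 10% against 0%: 0.1755 / 0.90 = 0.195, so 0.06 SD at r = 0.3 and 0.10 SD at r = 0.5.
- 15% against 5%: 0.2332 / 0.85 − 0.1031 / 0.95 = 0.274 − 0.109 = 0.166, so 0.05 SD at r = 0.3 and 0.08 SD at r = 0.5.

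A simulation of complete-case t-tests (24 per arm, 20,000 runs) agrees. With no true effect, the shift is 0.047 to 0.096 SD in these unequal, outcome-related cases, and between −0.005 and 0.001 SD when rates are equal (10%/10%) or r = 0. The false-positive rate in the unequal, outcome-related cases is 5.0% to 6.1%.

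**5. Upper bound.** If the 1, 2 or 3 most extreme of 24 values are removed from one arm and none from the other, and the flag is perfectly aligned with the outcome, that arm's mean shifts by 0.08, 0.16 or 0.22 SD.

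**6. Attrition, if these withdrawals count as dropping out.** Two withdrawals add 2/48 = 4.2 points overall, or 2/24 = 8.3 points within one diagnosis group if both fall there. Assume a flag rate per review of 1%, 2% or 5% over B1 to B3, independent of the 12%. Total attrition is 1 − 0.88 × (1 − p)³ = 14.6%, 17.2% or 24.6%. Keeping 42 completers would then need 50, 51 or 56 enrolled. If these withdrawals are not counted as dropping out, the attrition rate is unchanged.

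**The case against.** The strongest reply is that the rule may rarely be used and may do little harm. Veterans beyond the validity limits are already excluded at screening, and later withdrawal also needs compelling reasons. iTBS sessions are double-blinded, and of the allocation the plan says: "Randomization (SAS Proc Plan) will be managed by one un-blinded researcher who will not provide interventions or conduct testing". Arm-differential judgement is therefore less likely than in an open trial. This stands in part. It does not establish that the reviewing Neuropsychologist is blinded, and it cannot prevent differences between arms that treatment itself causes.

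Several stronger readings are tempting and are not supported:

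- **That the comparison is biased.** Step 4 shows that bias needs withdrawal that is both unequal by arm and related to outcome. Either condition alone gives about zero.
- **That 0.08 to 0.22 SD is the likely size.** It is a one-arm worst case with perfect alignment.
- **That Veterans are selected on the outcome itself.** The trigger is the validity scales and the outcome is the normed score: one instrument, different scores. The documents do not say how the two relate.
- **That attrition is inflated.** Section 5.6 does not say whether an investigator's withdrawal counts as dropping out. The Aim 3 test compares stroke with TBI, not Active with Placebo.

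It is also fair to say that whether invalid responding should end participation in a pilot is partly a matter of preference. That does not explain why performance-test data should stop being collected.

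**Conclusion.** The point holds as a design weakness that should be changed. The plan states affirmatively that Veterans will be withdrawn, without a threshold, a timepoint or stated blinding, and at B1 to B3 this follows treatment. The certain cost of each such withdrawal is the loss of all later measures, with no replacement.

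The bias is possible rather than established: about 0.05 to 0.10 SD with withdrawal of 10%/0% or 15%/5% and correlations of 0.3 to 0.5. That is small against the planned effect of 0.90. The power margin is thin: one withdrawal beyond the allowance leaves 80.2%, and the second takes it below 80%, assuming two-sided 0.05. The effect on attrition depends on a definition that the plan does not give.

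The documents contain no rate of atypical BRIEF-A scores, so every size here is conditional on the stated assumptions, except the data lost at each timepoint.

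**What to change.** In Section 5.5, apply the BRIEF-A validity limits as an exclusion at screening only. After randomization:

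- flag atypical BRIEF-A records by the same limits, with the reviewer blinded to arm;
- keep the Veteran in outcome follow-up and in the analysis of all randomized Veterans;
- repeat the BRIEF-A outcome analysis without flagged records, as a sensitivity analysis.

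In Section 5.6, report any investigator-initiated withdrawals separately from voluntary dropout in Aim 3.

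This concerns outcome collection and analysis only. Decisions on continuing treatment stay with the protocol's existing stopping and withdrawal rules.

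The cost is a change of wording and one extra analysis. The drawback is that some noisy BRIEF-A records remain in the main analysis, and the sensitivity analysis will show whether they matter.

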**Table 3 Potential Covariates**

Variable/Test	Operational Definition
Age at Study Enrollment	Mean or Median by diagnosis
Time post neurologic event	2 to 5 yrs. OR > 5 to 10 yrs.
# Comorbidities	≤ 3 or > 3
Etiology	Stroke: R/L hemisphere TBI: DAI + Contusion OR DAI + Contusion + Anoxia
Western Aphasia Battery-Screen	Likely OR Unlikely to have Aphasia
Boston Assessment of TBI -Lifetime	Lifetime score
Test of Pre-morbid Function	Normed Score
Marijuana	Medical, Recreational, None
Mood: Change in Anxiety	Mean Change
Mood: Change in PTSD symptoms	Mean Change by # and Mean Change in Severity
Mood: Change in Agitation	Mean Change

**Covariates.** To inform the need for stratified sampling in future research, we will collect a small set of Veteran-specific factors (Table 3) known or strongly thought to influence treatment responsiveness. Given evidence of positive correlations between age and stroke recovery as well as likelihood of further cognitive degradation and because prevalence rates dictate use of a wide age range, we will use average age. As comorbid conditions impede recovery or contribute to progressive cognitive degradation for both TBI and stroke, we have developed preliminary strata for comorbidities as well as time post event. These strata will be revised, as indicated by the sample distribution. For etiology, we will classify stroke as right or left hemisphere and TBI as: injuries resulting in diffuse axonal injury (DAI) and ≥ 1 contusion (e.g., blast, vehicular, assaults) or DAI + ≥ 1 contusion + an anoxic event subsequent to TBI (e.g., respiratory, cardiac). We will include pre-disability intellectual function, as measured with the Test of Premorbid Function, and likelihood of having any type of Aphasia, self-reported marijuana use and Lifetime TBI exposure. Measures obtained during PE testing will also be used to mood changes according to PTSD symptoms, depression, anxiety, and agitation.

**\*Suitability Measures.** To advance understanding of each Veteran's perspective of the appropriateness or suitability of that the number and type of tests and number of study-days, Veterans will rate the extent of their agreement to eight statements (Table 4).

**Table 4. Indices of Suitability**

1. The tests were all appropriate.
2. The number (#) of tests were just right.
3. There were too many tests.
4. I enjoyed participating in this study.
5. I disliked participating in this study.
6. I would recommend the study to a friend.
7. The # of study visits were just right.
8. There were too many study visits.

**Scale:** 1-Completely Disagree; 2- Disagree; 3- Neutral; 4-Agree; 5- Completely Agree

#### *Neuroimaging Data:*

Functional MRI measures will be collected at Baseline. Functional MRI measures will include structural imaging, 20 minutes of resting-state fMRI, diffusion tensor imaging (DTI) and an

Arterial Spin Labelling Sequence (ASL). Participants will be in the MRI for approximately 55 minutes. MRI scanning, for all participants, will take place at Northwestern University's CTI in the Olsen Pavilion located at [name].

*fMRI/Image Acquisition:* Scanning will take place on a Siemens Prisma 3.0 T MRI scanner equipped with a 64-channel head/neck coil. A high-resolution 3D MP-RAGE T1-weighted sagittal anatomical scan (voxel size = 0.8 mm isotropic resolution; 224 sagittal slices) will be collected for each participant. Resting state BOLD data will be collected using T2\* weighted EPI with a TR=0.5s, TE=25ms, flip angle of 48°, and 2mm isotropic voxels and a multiband factor of 8. Rest data will be collected while the subject views a fixation crosshair. The DTI data will use a two shell (64 directions per shell) acquisition with diffusion values of 1000 mm^2/sec. The acquisition will collect 1.5mm isotropic voxels with a TR=4500, TE=62ms and a multiband factor of 4, and 96 slices.

The collection of the fMRI data will be directed by [name]. fMRI data collected at CTI will be de-identified and uploaded to Northwestern University Research Image Processing System (NURIPS), an online collaborative research environment for securely storing, managing, analyzing and sharing de-identified medical imaging, associated data (e.g. behavioral), and results from advanced customizable processing pipelines. NURIPS is supported by both Northwestern University IT and Feinberg School of Medicine IT and takes advantage of the NU high performance computing cluster, Quest. NURIPS is a secure environment that supports the latest NU policy and procedures for encryption of data during transit and rest, provides granular project level access controls with varying permissions based on user groups, and allows non-NU collaborators access once they obtain an affiliate NetID. All data are backed up and have restore points that go back for 30 days. Once the data is uploaded to NURIPS, a copy will be downloaded onto Hines VA secure research servers for storage on <\\v12.med.va.gov\\v12\\hin>

*EEG:* For participant safety, all participants will complete a 30-minute baseline EEG sampling. EEG will not be routinely repeated unless clinically indicated. The EEGs will be interpreted by Epileptologists to confirm absence of seizure activity (i.e., epileptiform discharges).

## 5.6 Data Analysis

**Sample Size to Estimate Effect Sizes.** Our total sample size of 48 participants is based on 80% power to detect an Effect Size (ES) of .90. For 80% power, sample size per group to detect a small ES (0.35) is 130, for a medium ES (0.60) it is 42 and to detect a large ES (0.90) it is 21 per group. To estimate a large ES of 0.90, 42 subjects are required to achieve 80% power. Thus, we plan for 48 participants and 12% attrition.

Published methods  will be used to examine the merits of transdiagnostic sampling (Aim 1i). Specifically, we will use MLM to determine if neurologic diagnosis (stroke, TBI) moderates the effects of the Active intervention (Group 1: n = 24, Active iTBS and Active iTBS + APT; Group 2: n = 24, Placebo iTBS and Placebo iTBS + APT) on Maximum Cognitive Gain (MCG) as measured with the MDS and the AMPS.

For Aim 2, we will inform estimates of effect sizes by testing the idea (2i) that MDS gains and AMPS gains differ for Active iTBS and Active iTBS + APT. As specified in Table 1, we will examine if gains differ in magnitude by computing the MCGs for each outcome (MDS and AMPS) by each intervention. For each outcome, we will compare the Average Active iTBS MCG with the Average Placebo iTBS MCG and the Average Active iTBS + APT MCG with the

Average Placebo iTBS + APT MCG using t-tests for continuous data and z-tests for binary data. Using MLM, we will also determine if Active iTBS is related to more MDS or more AMPS gains. The group (Active iTBS or Placebo iTBS) by time interaction parameter will be used to examine if Active iTBS has a differential trend compared to Placebo iTBS. For 2i, we will also use MLM to identify presence of an additive effect of APT by examining Active iTBS + APT trend lines. For both the AMPS and the MDS outcomes, the group (Active iTBS + APT or Placebo iTBS + APT) by time interaction parameter will be used to examine if the Active iTBS + APT has a differential trend compared to Placebo iTBS + APT. For each intervention we will also determine (2ii) presence of persisting effects of Active iTBS and Active iTBS + APT in the short-term, long-term and cumulatively. Using the PE measures specified in Table 1 and t-tests, we will compare each PE measure for Active iTBS with Placebo iTBS and for Active iTBS + APT with Placebo iTBS + APT. Significant results will be reported. For (2iii), we will use one-tailed t-tests to identify presence of practice effects for MDS and AMPS. We will compare MDS and AMPS average peak gains after Placebo iTBS with average peak gains after Active iTBS. If the average Placebo iTBS peak gain is greater than the average Active iTBS peak gain for either MDS or AMPS, then we will repeat analyses above (for 2i and 2ii) using ImE and PE measures after adjusting them for the detected practice effects.

For Aim 3, we will compute study attrition as percent of participants dropping out after Study-Day 2 and after Study-Day 3. We will examine whether or not these attrition rates differ (3i) by stroke and TBI groups using chi-square. To examine if Veteran's with stroke and TBI have (3ii) different perceptions regarding the suitability of the number and type of tests and number of study-days, we will compare each group's average ratings, by suitability index, using t-tests. To explore the relationship between perceived suitability and fatigue as well as mood (3iii), we will compute Pearson correlations at each of the 5-timepoints (B0 through B4) between average ratings of suitability indices 1 through 3 and averages for each of the two fatigue measures and each of the five mood measures [5x (3x2) + 5x (3x5) = 105 correlations]. We will also compute correlations for average suitability indices 7 through 8 collected on Study-Day 4 (B4) with the averages from that same day for each of the two fatigue measures and each of the five mood measures [1x (2x2) + 1x (2x5) = 14 correlations]. We will test the significance of each correlation using Fisher Z test and results will be interpreted accordingly.

Aims 2 and 3 involve multiple comparisons. Bonferroni correction of type I error rate is very conservative, and, at this early research stage, it could mask important findings. Thus, we will control for false discovery rate (FDR) using an FDR level of .05.

For Aim 4 we will identify the optimal iTBS Neural Targets using GIMME, which is a directed functional connectivity modeling approach based on iterative model optimization. The optimal brain target is the region that, when modulated, communicates effectively with the neural systems supporting cognition such that it leads to improved cognitive abilities. This target could be a brain region defined at the group level (i.e., generalizable to mild TBI+PTSD population), the subgroup level (specific to mild TBI+PTSD persons with shared features), or at the individual level. GIMME is based on a feed forward method of adding paths among the pre-specified brain Regions of Interest (ROIs) that serve as a fixed anatomical structure. Considering that GIMME models have included 7 to 20 ROIs, the fixed GIMME anatomical structure will include a set of 12 ROIs implicated in cognition and that serve as nodes in neural networks based on a parcellation atlas will be used in all GIMME models to as the fixed anatomical structure. (Table 5). The threshold for a group-level or sub-group-level pathway connection can be manipulated but we will use 75% as it has been determined to work well. Based on the fixed anatomical structure, GIMME first produces a group-level model of the ROI structure common to at least 75% of the persons in the full dataset/sample.

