**Study-Day 2 (4 days after Study Day 1)(~8 hours):**

- 1. PE testing battery
- 2. A single session of **Active** iTBS or **Placebo** iTBS
- 3. Randomly assigned ImE test (MDS or AMPS), administered 3-times at 30 min intervals, each interval includes 5 to 15 min of rest).
- 4. PE testing battery
- 5. Suitability ratings 1-3

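### The single 80% power figure at ES 0.90 fits full-arm comparisons but not the Aim 2i immediate-effect t-tests on MDS, which have about 12 Veterans per arm and about 56% power

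*Combined protocol and SAP*

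**What the plan says.** Section 5.6 opens its sample-size paragraph with the label "Sample Size to Estimate Effect Sizes" and gives one operative calculation: "Our total sample size of 48 participants is based on 80% power to detect an Effect Size (ES) of .90". It adds that "to detect a large ES (0.90) it is 21 per group", hence 42 in total, raised to 48 for 12% attrition. Alpha, sidedness and outcome are not stated. The arms are 24 Active and 24 Placebo.

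For Aim 2i the same section plans separate tests by outcome and by intervention: "For each outcome, we will compare the Average Active iTBS MCG with the Average Placebo iTBS MCG", then the Active iTBS + APT average against the "Average Placebo iTBS + APT MCG using t-tests for continuous data". Mixed models are planned as well: "The group (Active iTBS or Placebo iTBS) by time interaction parameter will be used to examine" a differential trend.

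Section 5.1 determines who supplies these data. Within each iTBS group, Veterans "will be randomly assigned to be tested with the Modified Digit Span (MDS) or AMPS". The Study-Day 2 schedule lists "Randomly assigned ImE test (MDS or AMPS), administered 3-times at 30 min intervals", and Study-Day 3 uses the other test. The PE battery goes to everyone at five timepoints. Section 5.5 and Table 2 include AMPS in that battery; the MDS appears only as an ImE measure.

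For Aim 1, Section 3.0 expects that diagnosis will not moderate the Active effect on MCG, and Section 5.6 tests this by mixed model. No power, precision or rule for reading a null result is given.

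**The concern.** One power figure tied to no outcome will be read as covering the planned tests, including the MDS and AMPS gain comparisons. The link is easy to make: the one published effect near 0.90 that the protocol quotes (g = .938, Section 5.5) is for immediate working-memory gains in healthy controls and is the rationale for using the MDS. Section 5.6 does not cite it, so that link is an inference.

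The design gives each ImE test to only part of each arm per session, so those comparisons are smaller than the ones the 80% describes. A non-significant MDS result could be taken as evidence against a large effect when the test had little better than an even chance of finding one. Whoever plans the follow-on cross-over study would also work from estimates less precise than the sample-size paragraph suggests.

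Aim 1 raises a related problem. The expected result is a null interaction, and an interaction is estimated less precisely than a main effect from the same Veterans.

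**Working it through.** **Inputs from the documents.** ES 0.90, 80% power, 21 per group, 48 enrolled, 12% attrition, arms of 24 and 24 (Section 5.6). One ImE test per Veteran per session, and 24 stroke and 24 TBI spread equally over the arms, so 12 per diagnosis-by-arm cell (Section 5.1).

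**Assumed or inferred.** An even MDS/AMPS split, 24/2 = 12 per arm per test; the available text gives no ratio and Figure 2 is not shown. Two-sided 0.05, inferred because it reproduces 21 per group (one-sided needs 16). ES is in units of the SD of the gain, analysed as continuous.

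**Formulas, n per arm.** SE of the arm difference = √(2/n) SD; noncentrality = 0.90/√(2/n); df = 2n − 2; power from the noncentral t; 95% CI half-width = t(0.975, df) × √(2/n).

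**1. The plan's own figure.** Required n is 20.4, so 21 per group and 42 in total; 42/0.88 = 47.7, so 48. At n = 21 the noncentrality is 0.90/0.309 = 2.92 with 40 df, and power is 81.2%. The statement is correct for full arms.

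**2. MDS t-test at one session.** At n = 12 the SE is √(2/12) = 0.408, the noncentrality 0.90/0.408 = 2.20, df 22. Power is 55.9% (68.8% one-sided). Half-width: 2.07 × 0.408 = 0.85 SD.

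**3. Attrition.** Section 5.7 replaces Veterans who withdraw before any post-baseline procedure, and Aim 3 counts dropout after Study-Day 2, so Study-Day 2 stays near 12 per arm. If all 12% is lost before Study-Day 3, 12 × 0.88 = 10.6 per arm.

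| Comparison | n per arm | Power at ES 0.90 | ES detectable at 80% | 95% CI half-width (SD) |
|---|---|---|---|---|
| Full arms, as enrolled | 24 | 86.3% | 0.83 | 0.58 |
| Full arms, after attrition | 21 | 81.2% | 0.89 | 0.62 |
| MDS, one session | 12 | 55.9% | 1.20 | 0.85 |
| MDS, Study-Day 3, after attrition | 11 | 52.0% | 1.26 | 0.89 |
| MDS, Study-Day 3, after attrition | 10 | 47.8% | 1.32 | 0.94 |

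**4. Uneven splits.** With 10 and 14 per arm on the two tests, power is 48% at 10 vs 10 and 63% at 14 vs 14. With 8 and 16 it is 39% and 69%. No two-sided case reaches 80%.

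**5. Multiplicity.** Section 5.6 controls the false discovery rate at .05 for Aims 2 and 3, which can only lower per-test power. The amount depends on the test family. As an illustration, a per-test alpha of 0.0125 at 12 vs 12 gives 33%.

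**6. Aim 1 interaction.** With four cells of size c, SE = √(4/c) SD and df = 4c − 4. Pooling sessions, c = 12: SE 0.577, half-width 2.015 × 0.577 = 1.16 SD. Power is 33% for a 0.90 SD benefit in one diagnosis and none in the other; 80% power needs an interaction of about 1.65 SD. In a single session under the even split, c = 6: SE 0.816, half-width 1.70 SD, power 18% at 0.90 SD.

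**The case against.** **This is a pilot.** The paragraph is labelled as sizing for effect-size estimation, and the study can deliver estimates whatever the power. That limits the consequence. But precision is what an estimation study has to offer, and for the MDS it is 0.85 SD against 0.58 to 0.62 SD for full arms.

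**AMPS may not be affected.** All participants have PE AMPS before and after each session. An AMPS gain built only from those administrations could use full arms. Section 5.6 points to Table 1 for how MCG is obtained, but Table 1 holds the eligibility criteria, so the available text does not settle this. The objection stands for AMPS: the 56% is conditional there. It does not help the MDS, which is not in the PE battery. WAIS-IV Digit Span, taken on everyone, softens the loss for working memory but is not the planned MDS comparison.

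**Sidedness.** Aim 2iii uses one-tailed t-tests, so one might suppose the same for Aim 2i. The text does not say so, 21 per group reproduces only as two-sided, and one-sided power at 12 vs 12 is still 69%.

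**Stronger readings that a reader might infer.** The ES 0.90 calculation is not wrong: it reproduces. Nor do all Aim 2 comparisons fall short, since the PE t-tests use full arms. The mixed-model trend analyses cannot be called underpowered from these figures, because their power depends on within-person correlations that the documents do not give.

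**Conclusion.** The concern holds in limited form. The 80% at ES 0.90 is right for full-arm comparisons (81% to 86%, before FDR control) and wrong for the Aim 2i ImE t-tests on the MDS. Those have about 56% power and a detectable ES of about 1.20, falling to 48% to 52% and 1.26 to 1.32 on Study-Day 3 if all attrition comes first. The same applies to AMPS only if its MCG uses the ImE administrations. The result rests on the even split and the inferred two-sided 0.05; neither the uneven splits tried nor a one-sided test at 12 vs 12 brings every MDS comparison to 80%.

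For Aim 1, a non-significant interaction would be the likely result even if the whole 0.90 SD benefit lay in one diagnosis: at 33% power it would be missed about two times in three. A reader might take a null result as evidence against a benefit confined to stroke or to TBI; this sample would not support that. Nor should the 1.16 SD half-width be taken as the size of difference the study can reliably detect, which is about 1.65 SD.

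**What to change.** **Section 5.6, sample-size paragraph.**
- Limit the 80% figure to full-arm comparisons, and name the alpha and sidedness used.
- State separately for the MDS ImE t-tests, and for AMPS if its MCG uses the ImE administrations: about 12 per arm, about 56% power at ES 0.90, detectable ES about 1.2 (1.26 to 1.32 on Study-Day 3 if all attrition precedes it).
- Name the MDS/AMPS split, as shown in Figure 2 if it is there and otherwise as an assumption.
- Note that FDR control lowers power further and that the mixed-model analyses are not covered by these figures.

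**Section 5.6, Aim 1.** Report the diagnosis-by-arm interaction with its 95% CI, and state that a non-significant result alone will not be read as showing no moderation.

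**Cost.** Wording only: no added participants, procedures or equivalence margin. The stated power for these t-tests becomes less favourable.
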